7.14	Data Monitoring Committee.....	29
8	Ethical and Regulatory Aspects.....	29
8.1	Responsibilities of the Investigator	29
8.2	Subject Information and Informed Consent	30

8.3	Subject Identification and Privacy.....	31
8.4	Independent Ethics Committee or Institutional Review Board	31
8.5	Health Authorities.....	32
9	Trial Management.....	32
9.1	Electronic Case Report Form Handling.....	32
9.2	Source Data and Subject Files	32
9.3	Investigator Site File and Archiving.....	33
9.4	Monitoring, Quality Assurance and Inspection by Health Authorities	33
9.5	Assessment of Clinical Investigators and Sites	33
9.6	Trial Training.....	34
9.7	Required Trial Equipment	34
9.8	Site Activation and Supply of Trial Materials.....	35
9.9	Changes to the Clinical Trial Protocol.....	35
9.9.1	Clinical Trial Report.....	35
9.10	Publication	36
10	Intellectual Property.....	36
11	Trial or site Discontinuation	37
12	Trial Closure	37
13	References.....	37

List of Abbreviations

AE	Adverse Event
AFC	Antral Follicular Count
AMH	Antimullerian Hormone
ART	Assisted Reproductive Technologies
B	Blastocyst
CE	European Community
CRF	Case Report Form
CRO	Contract Research Organization
CSL	Clinical Science Liaison
EB	Early Blastocyst
EC	Ethics Committee
eCRF	Electronic Case Report Forms
EDC	Electronic Data Capture
EEVA H/M/L	Eeva Predicted High, M: Medium, L: Low
ET	Embryo Transfer
EU	European Union
GP	General Practitioner
hCG	Human Chorionic Gonadotropin
HFEA	Human Fertilisation and Embryology Authority – UK
ICF	Informed Consent Form
ICH	International Committee on Harmonisation
ICSI	Intracytoplasmatic Sperm Injection
IEC	Independent Ethics Committee
INN	International Nonproprietary Name
IRB	Institutional Review Board

ITT	Intention to Treat
IVF	In Vitro Fertilization
NCA	National Competent Authorities
PN	Pronuclei stage
SAP	Statistical Analysis Plan
SPC	Summary of Product Characteristics
USA	United States of America

1 Synopsis

Trial title	A Phase IV, prospective, randomized, exploratory, multicenter, Eeva trial (Time Lapse Eeva – TiLE)
Trial number	EMR700623 545
Sponsor	Merck KGaA, [name]
Trial type	Prospective, randomized, multicenter Trial
Coordinating Investigator	PPD
Trial center(s)/country(ies)	Approximately 20 Centers in 8 Countries: Canada, Germany, Italy, France, Norway, Sweden, Spain, UK
Planned Trial period	April 2015 – March 2017
Trial objectives	
Primary Objective:
 
To compare the implantation rate for Day 3/5 embryo transfers using Eeva scores plus morphology grading versus Day 3/5 embryo transfers using morphology grading only.
 
Secondary Objectives:
 
To compare the following outcomes from the Eeva trial group to the control group.
 
 • Clinical Pregnancy • Ongoing pregnancy rate • Multiple pregnancy rate. • Miscarriage rate. • Utilization rate.
Trial design and plan	Prospective, randomized, exploratory, multicenter trial. When approximately 50% of the subjects have implantation results, an interim analysis will be performed.
Planned number of subjects	1500

Diagnosis and main inclusion and exclusion criteria	
All IVF/ICSI patients according to the eligibility criteria:
 
For inclusion in the trial, all of the following inclusion criteria must be fulfilled:
 
1. All infertile patients treated with IVF/ICSI.2. Patient age \leq 40 years.3. \leq 3 failed IVF/ICSI cycles.4. At least 4 normally fertilized eggs (2PN) in current cycle.5. Normal uterine cavity.6. Fertilization using only ejaculated sperm (fresh or frozen).7. Subject must have read and signed the Informed Consent form. 
Subjects are not eligible for this trial if they fulfill any of the following exclusion criteria:
 
1. Have clinically significant systemic disease.2. Have abnormal, undiagnosed gynecological bleeding.3. Have any contraindication to Controlled Ovarian Stimulation (COS) for ART and to gonadotropins to be used in ART.4. Egg donor cycle.5. Planned “freeze all” cycle (oocytes or embryos).6. Concurrent participation in another clinical trial.
--	--

Investigational Medicine Product	Not applicable.
Investigational Medical Device	EEVA, a type-II medical device that received the CE marking in a de novo process as a diagnostic device
Planned duration of observation for each subject	Embryos of consented subjects will be assessed with EEVA System and morphological assessment and after ET will be follow-up until achievement of implantation and confirmation of pregnancy.
Primary endpoint(s)	Implantation rate from embryos transferred on day 3 or 5.
Secondary endpoint(s)	Utilization rate, Clinical pregnancy, Ongoing pregnancy, Multiple pregnancy and Miscarriage.
Estimated Trial calendar	FPI: 29-JUN-2015 LPI: 31-OCT-2016 LPLV: 31-DEC-2016 Trial Report Date: 30-APR-2017

2 Sponsor, Investigators and Trial Administrative Structure

The Sponsor(s) of the trial is Merck KGaA, [name].

It is planned to perform the trial at approximately 20 sites in about 8 countries from Europe (EU) and Canada (CA).

Principal Investigator: PPD [REDACTED]

PPD [REDACTED] is the Contract Research Organization (CRO) appointed for trial management including monitoring activities.

[REDACTED] PPD [REDACTED], will provide the database for electronic data capture (EDC), randomization process and electronic case report form (eCRF) management support. Statistical analysis will be done by PPD [REDACTED] [REDACTED].

Trial will be managed by Global Medical Affairs in coordination and with the support from Merck KGaA Global Clinical Operations group and countries Medical Affairs personnel.

3 Background Information and Trial Rationale

This clinical protocol describes the requirements for the Eeva technology (Early Embryo Viability Assessment) EU/CA post-marketing trial. The purpose of this trial is to use Eeva per the approved European commission (CE) mark labeling and gather additional data to evaluate the efficacy to predict embryo implantation potential, for the future development of this technology. This trial will be conducted using a standardized protocol at approximately 20 centers in the European Region and Canada.

As the sponsor of this clinical trial, Merck KGaA has the overall responsibility to conduct this post-marketing trial, including assurance that the trial will be performed according to the clinical protocol, applicable regulations and standards, the Declaration of Helsinki, and elements of Good Clinical Practices (GCP) as may be applied to medical devices.^{1,2} The confidentiality provisions of all applicable laws and regulations will apply throughout.

Eeva technology and the Eeva petri dish are classified as a class IIa medical devices in the European Union (CE marked), United States and Canada, commercially available.

Eeva is a time lapse monitoring system with an integrated software, which is able to take photos of embryos every 5 minutes during embryo culture and embryo development. The high quality images collected are automatically analyzed and validated by the software to define precise timing of cell divisions and based on a proprietary algorithm, make a recommendation that is provided to the user to determine the likelihood of whether or not an embryo will develop to the

blastocyst stage. The user has the ability to export image data, embryo reports, and movies. The images are acquired while embryos are developing inside standard incubators. In case of any Eeva malfunction the subsequent development of the embryos will not be affected in any way and the only missing piece will be the automatic recommendation by the computer.

The optimal goal of IVF/ICSI should be the delivery of a healthy singleton baby.³⁻⁵ The clinical dilemma, is how to reduce the number of embryos for transfer to prevent multiple births while at the same time maintaining or improving IVF/ICSI success rates.

Currently, embryos are being selected based on traditional morphology scores developed in the early 1980s, which are based on multiple observations of embryos under regular light microscopes.⁶⁻⁹ However, it is that traditional morphology grading, which only captures static images at a few time points, is of very limited predictive value. It was reported that only 51% of embryos transferred on Day 5 were pre-selected for transfer on Day 3.¹⁰ In a controlled Trial, embryologists were asked to choose 2 embryos with optimal potential for blastocyst development using traditional morphology grading criteria. Results showed that morphology criteria assessed on Day 3 did not accurately predict blastocyst formation. In 39% of cycles neither choice resulted in blastocyst formation, and in 38% of cycles 1 assessment resulted in a blastocyst transferred. Embryologists were able to pick the best 2 embryos in just 23% of cycles.¹¹

Recently, researchers from Stanford University reported results that correlated time-lapse image analysis with gene expression profiling of pre-implantation human embryo development.¹² It was discovered that success in development to the human blastocyst stage can be predicted accurately from dynamic, non-invasive imaging parameters that are observed prior to embryonic genome activation (on Day 3). These parameters can be reliably measured by way of automated image analysis, confirming that successful development follows a set of carefully orchestrated and predictable events. Moreover, image phenotypes reflected underlying molecular programs of the embryo and individual blastomeres. This was the first trial to report that dynamic morphology parameters of embryo development reflect underlying molecular program status and provide a promising platform for early assessment of embryo viability.¹²

Eeva was developed to translate the significant findings from the research trial to the clinical setting.¹² The benefit demonstrated during the clinical investigation of the Eeva System Trial was that Eeva may assist the embryologist in improving embryo assessment accuracy by predicting blastocyst formation at cleavage stage with a specificity of 85%.¹³ That is, out of all Non-Blastocyst (arrested) embryos, Eeva was able to identify 85% of them. The main limitation in traditional morphology is its high sensitivity and low specificity. Currently, any embryo with good morphology is considered to be “viable.” However, clinical results have shown that many embryos selected by good Day 3 morphology criteria are false positives.^{7,8} Embryologists are in need of a test which can discriminate – particularly among the embryos with good morphology – those which *are truly viable and will form blastocysts*. The high specificity of Eeva system’s determines which good morphology embryos will actually arrest. Therefore, Eeva is a useful complement to aid the embryologist in identifying the most viable embryos for transfer.

3.1 Benefit-risk assessment

The analysis of the risks and benefits demonstrated that, the Eeva System met its safety and performance requirements and the device fulfilled its intended use as claimed by Merck KGaA Fertility Technologies. Following is a description of potential (expected) risks and benefits that may be associated with use of Eeva technology. Eeva received the CE marking in a de novo process as a diagnostic device.

3.1.1 Risks Related to Eeva

Indeed, there are no risks related with Eeva utilization that could potentially affect embryos survival or quality due to the fact that any malfunction on the Eeva system will only affect its ability to take pictures of the embryos in culture but will not affect in any way the temperature, gas environment and/or culture media conditions to which the embryos will be exposed during the incubation process. In Eeva clinical investigation studies, the average blastocyst formation rate in subjects who had embryo transfers at the blastocyst stage was 47.4%. This demonstrated that embryos imaged by Eeva did not have their development to blastocyst stage altered given the average rate reported in the literature for blastocyst formation is approximately 45.4%.¹⁷

3.1.2 Benefits of Eeva

The benefit demonstrated during the first clinical investigation was that the Eeva System can assist the embryologist in improving embryo assessment accuracy by predicting blastocyst formation at cleavage stage with a specificity of 85%. That is, out of all arrested embryos, Eeva was able to identify 85% of them.¹³

An additional benefit is that the Eeva System generates consistent and objective data which help embryologists to be more standardized while performing embryo assessments. Furthermore, the Eeva System provides a tool that is fully automated, real-time, and can be easily implemented in the IVF/ICSI laboratory and fit into the work flow.

4 Trial Objectives

The aim of this trial is to use Eeva per the approved, CE mark labeling and gather additional data to evaluate the efficacy to predict embryo implantation potential when combined with morphological assessments.

4.1 Primary

The primary objective of the trial is to compare the rate of implantation for Day 3/5 embryo transfers using Eeva scores plus morphology grading versus Day 3/5 embryo transfers using morphology grading only. Implantation rates are calculated by dividing the number of gestational sacs with fetal heart beat identified by ultrasonography at weeks 5 to 8 by the number of embryos transferred on Days 3 or 5.

4.2 Secondary

The secondary objective is to compare the following outcomes from the combined Eeva + morphology results vs. the control (morphology only) group: Utilization Rate (number of transferred and frozen embryos divided by number of normally fertilized oocytes x100), Clinical Pregnancy (assessed by ultrasonography at weeks 5 to 8), Ongoing pregnancy rate (assessed by ultrasonography at weeks 10 to12), Multiple pregnancy rate (assessed by ultrasonography at weeks 5 to 8) and spontaneous miscarriage.

5 Investigational Plan

5.1 Overall Trial Design and Plan

In general, the Eeva EU/Canadian trial will include 22 investigational sites. Each site will conduct the trial using the same clinical protocol.

Recruitment of patients at each site, with subjects who voluntarily consent to participate, is expected to continue for up to 9 months. Additional follow-up after embryo transfer will take place up to Day 12-18 days to verify biochemical pregnancy and at 5-8 gestational weeks to verify clinical pregnancy. Additionally, pregnancy outcomes will be collected via eCRF for subjects who were pregnant at the 5-8 week gestational follow-up visit (or subsequent ultrasound results). Total duration of the trial, including start up and close out activities, is approximately 19 months. Desired follow-up endpoints and additional collection of outcomes like spontaneous miscarriage is not being considered in the timeline for completion.

5.2 Discussion of Trial Design

The prospective, randomized, exploratory design selected for this trial was defined based on the need to test new diagnostic technologies, like Eeva, to assess embryo viability by collecting real life clinical data and compare it with a control. Implantation rate of individual embryos using the technology will be explored to define realistic confidence intervals utilized for the generation of strong hypothesis to be validated in future RCT.

5.3 Selection of Trial Population

Subjects for this trial are IVF/ICSI patients to be enrolled according to the eligibility criteria.

5.3.1 Inclusion Criteria

For inclusion in the trial, **all** of the following inclusion criteria **must** be fulfilled:

1. All infertile patients treated with IVF/ICSI.
2. Patient age \leq 40 years.
3. \leq 3 failed IVF/ICSI cycles.
4. At least 4 normally fertilized eggs (2PN) in current cycle.
5. Normal uterine cavity.
6. Fertilization using only ejaculated sperm (fresh or frozen).
7. Subject must have read and signed the Informed Consent form.

5.3.2 Exclusion Criteria

Subjects are not eligible for this trial if they fulfill **any** of the following exclusion criteria:

1. Have clinically significant systemic disease.
2. Have abnormal, undiagnosed gynecological bleeding.
3. Have any contraindication to Controlled Ovarian Stimulation (COS) for ART and to gonadotropins to be used in ART.
4. Egg donor cycle.
5. Planned “freeze all” cycle (oocytes or embryos).
6. Concurrent participation in another clinical trial.

5.4 Recruitment of Participants

Subjects will be recruited from patients undergoing IVF/ICSI treatment cycles at the investigators’ clinics. Patients will be assessed according the Inclusion/ Exclusion criteria to determine their eligibility for participation.

5.5 Criteria for Randomization

All eligible subjects will be assigned to the group of subjects with embryo transfers using Eeva scores plus morphology grading and to group of subjects with embryo transfers using morphology grading only by randomization. A permuted block randomization with fixed block size and allocation ratio of 2:1 will be used. Further details of the procedure will be described in the EDC related manuals.

An allocation ratio of 2:1 is used since this is an explorative trial. The main objective is to collect data of first experience with the EEVA Time Lapse system. To generate hypotheses in comparison to the ‘morphology grading only’ group comparable data of the morphology grading only need to be collected.

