7.1 Predetermination of Sample Size

7.2 Sample Size

This is an exploratory trial to generate hypotheses for future confirmatory clinical trials.

It is planned to enroll 1000 subjects in the group of subjects with embryo transfers using Eeva scores plus morphology grading and 500 subjects into the control group of subjects with embryo transfers using morphology grading only. Enrollment is non-competitive, each center selected to participate in the study is expected to enroll a minimum number of patients to be defined at site start-up.

Based on this number of subject's precise estimates of the primary endpoint, the rate of implantation for Day 3/5 embryo transfers, is possible.

The following table shows for different implantation rates the distance from the rate (proportion) to the limit of a 95% confidence interval.

Implantation rate	Distance to limit of 95% CI	
	500 subjects	1000 subjects
25%	3.8	2.7
30%	4.0	2.8
35%	4.2	3.0
40%	4.3	3.0
45%	4.4	3.1

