7.13 Data Collection

Merck KGaA will use an electronic data capture (EDC) system to collect subject data. The electronic case report forms (eCRFs) are the primary component of EDC that the site personnel will interface with. Training on use of the system will be provided to the trial site personnel. Instructions for completion of the eCRFs also will be provided.

The eCRFs must be completed, saved, and locked via electronic signature by the investigator using a unique ID and password. This ID and password are for the use of the investigator only and may not be used by any other person. Because of the potential for errors or inaccuracies in transcribing data into eCRFs, source documentation must be maintained in each subject's hospital/clinic chart and/or electronic medical record. The eCRFs and source documentation must be available at all times for inspection by the monitors or regulatory inspectors.

Required data will be recorded on the appropriate eCRF at the time of or as soon as possible after the subject visit or embryo assessment. The eCRF data will be processed through an EDC database. Questions about completion of the eCRFs may be directed to the Merck KGaA/PPD clinical trial team.

Eeva embryo pictures (1 picture every 5 minutes of culture over 3/5 days) will be anonymous and collected by Merck KGaA Clinical Application Engineer (CAE) twice during the duration of the study. These pictures will be sent to the bioanalytical department from PPD to explore the possibility to strengthen the predictive algorithm.

Changes made to eCRFs will be electronically recorded in a complete audit trail that cannot be changed, but can be accessed by authorized personnel at any time. All data are transmitted via the internet in an encrypted fashion. When received at the server site, the data are decrypted and stored. Data can be extracted for Merck KGaA review and analysis at any time.

It is the responsibility of the investigators and the trial staff to complete the eCRFs accurately and in a timely fashion. The principal or designated trial investigator will sign and date each eCRF to verify that the data has been reviewed by him/her.

This trial will not have blinding procedures as subject cohorts will be assigned to each arm according to the procedure described.

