8.2 Subject Information and Informed Consent

An unconditional prerequisite for a subject's participation in the trial is his/her written informed consent.

To protect the rights and welfare of trial subjects, the trial will be conducted in conformance with the Declaration of Helsinki and elements of good clinical practices as may be applied to medical devices.^{1,2} The confidentiality provisions within all applicable laws and regulations will apply throughout. Obtaining informed consent in accordance with the policy of the EC, this clinical protocol, and applicable regulations is mandatory for subject participation. The sponsor will avoid improper influence on or inducement of the subject for participating in the trial. The subject informed consent document(s) must be provided in a language that the patient reads and understands. All subjects must provide voluntary, written informed consent prior to the start of any trial-related activities. This includes subjects who are the partners of the subjects, if applicable.

Informed consent should be signed prior to the day of oocyte pick up, preferably on the day of the last ultrasonography for assessment of number of follicles available. On day 1 after oocyte pick up and following assessment of the number of 2PNs available, subjects will either be enrolled in the trial or not included in the trial.

Adequate information must therefore be given to the subject by the Investigator before informed consent is obtained (a person designated by the Investigator may give the information, if permitted by local regulations). A subject information sheet in the local language will be provided by the Sponsor for the purpose of obtaining informed consent. In addition to providing this written information to a potential subject, the Investigator or his/her designee will inform the subject verbally of all pertinent aspects of the trial (*the language used in doing so must be chosen so that the information can be fully and readily understood by laypersons*). Depending on national regulations, a person other than the Investigator may inform the subject and sign the Informed Consent Form.

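### The protocol fixes the block size at 2:1 in an unblinded trial with enrolment on Day 1; if blocks are kept per site, sites could foresee a material share of allocations, and varying the block size is a cheap safeguard.

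*Protocol*

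**What the plan says.** Protocol Section 5.5 states "A permuted block randomization with fixed block size and allocation ratio of 2:1 will be used", and Section 7.3 repeats it. Section 5.5 then adds: "Further details of the procedure will be described in the EDC related manuals". So the protocol itself decides that the size is fixed. It leaves open the value, whether blocks are kept by centre, and how the allocation is concealed. SAP Sections 5.3 and 6 refer back to Protocol Sections 5.3 and 5.6, which do not settle these points.

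Section 7.13 says of blinding: "This trial will not have blinding procedures as subject cohorts will be assigned to each arm according to the procedure described". Section 8.2 asks for consent before the day of oocyte pick-up and places entry on Day 1: "following assessment of the number of 2PNs available, subjects will either be enrolled in the trial or not included in the trial".

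Two statements pull the other way. Section 5.5 opens with "All eligible subjects will be assigned to the group of subjects with embryo transfers using Eeva scores plus morphology grading" or to morphology grading only, by randomization. Section 2 says a vendor provides the database for data capture together with the "randomization process and electronic case report form (eCRF) management support".

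**The concern.** Three stated features combine. Staff see every allocation made at their own site. They hold prognostic information, the 2PN count, when a consented woman is entered or left out. A constant block length lets anyone who knows it, and who can see the whole block, work out the remaining slots once one arm's share is used up. The 2:1 ratio also requires a block length that is a multiple of 3, so there are few values to guess.

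If an expected allocation influenced who was entered, the arms would differ in prognosis from the start, and a larger sample would not remove that. Protocol Section 4.1 makes comparison the primary objective, and Section 7.6.2 plans an exploratory Poisson comparison. SAP Section 14.1 drops inference for the primary analysis but still reports the arms side by side. SAP Section 14.6 plans a regression on treatment and subgroup risk ratios with P values. That regression adjusts for age, day of transfer, stimulation protocol, drugs, culture medium and centre, but not for the 2PN count.

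**Working it through.** **Inputs from the documents.** Fixed blocks at 2:1 (Protocol 5.5, 7.3). 1000 + 500 = 1500 women (7.2). About 20 sites (Section 2; Section 5.1 says 22), so 1500/20 = 75 women per site.

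**Assumptions, because the documents are silent.** Block lengths of 3, 6, 9 and 12, and either one list per site or one central list.

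**Step 1: the plan's own figure.** The table in Section 7.2 gives the distance to the 95% confidence limit, 1.96 × √[p(1−p)/n]. At p = 35% this is 4.18 points for n = 500 and 2.96 for n = 1000; the table prints 4.2 and 3.0. All ten entries reproduce. The documents give no figure on predictability. For scale, the half-width for the difference between arms at 35% is 1.96 × √[0.35 × 0.65 × (1/500 + 1/1000)] = 5.1 points, counting one unit per subject.

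**Step 2: blocks kept per site, length known.** Let a block hold m Eeva and c control slots, with m = 2c. An allocation is certain once the other arm's slots are used up, so the certain slots are the closing run of one arm. Expected certain slots per block = m/(c+1) + c/(m+1). For length 3 this is 2/2 + 1/3 = 1.333, and 1.333/3 = 44.4%.

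| Length | m, c | Certain per block | Share certain | Of 1500 | Best guess correct |
|---|---|---|---|---|---|
| 3 | 2, 1 | 1.333 | 44.4% | 667 | 77.8% |
| 6 | 4, 2 | 1.733 | 28.9% | 433 | 74.4% |
| 9 | 6, 3 | 1.929 | 21.4% | 321 | 72.8% |
| 12 | 8, 4 | 2.044 | 17.0% | 256 | 71.7% |

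Always guessing Eeva is right 66.7% of the time.

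**Step 3: one central list, 20 equal sites, each seeing only its own allocations.** Simulation gives 1.7% certain for length 3, 0.05% for length 6 and essentially none for 9 and 12. It credits the site with knowing where each block starts, which is generous. Hand check for length 3:
- second slot: (1/20)(1/3) = 0.0167
- third slot: (1/20)(2/3) + (1/400)(1/3) = 0.0342
- total 0.0508 over three slots, or 1.7%

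**Step 4: randomly varying lengths within site.** Simulation of 75 women per site, with an observer who knows the set of lengths but not the order:

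| Lengths | Certain | Predictable with at least 90% probability |
|---|---|---|
| 3, 6 | 9.5% | 34% |
| 6, 9 | 5.4% | 16% |
| 3, 6, 9 | 3.9% | 13% |
| 6, 9, 12 | 2.3% | 9% |

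Fixed lengths simulated in the same way give 44%, 28%, 20% and 16% certain for 3, 6, 9 and 12.

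**Step 5: illustration of the stake (assumed, not a forecast).** With per-site blocks, suppose women entered on certain Eeva slots have an implantation rate d points above average, and those on certain control slots d points below. The arm difference shifts by d × [1/(c+1) + 1/(m+1)]. With d = 5 and every certain slot used, the shift is 4.2, 2.7, 2.0 or 1.6 points for lengths 3, 6, 9 and 12. If one certain slot in ten is used, it is 0.4, 0.3, 0.2 or 0.2. Doubling d doubles these. Neither d nor the fraction used comes from the documents.

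**The case against.** The strongest reply is that the documents never establish foreseeability. They do not say that blocks are kept per site, and they give no length. A vendor runs the randomization, and the manuals that hold the detail are not part of the public plan. Under one central list the concern almost vanishes.

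The Day 1 step can also be read as an eligibility check, not a free choice. At least four normally fertilised eggs is inclusion criterion 4, consent has already been signed, and all eligible subjects are to be assigned. Passing over an eligible, consented woman would depart from the protocol. Finally, the trial is exploratory, and presentation by method used (Protocol 7.5, SAP 8.1) already departs from the randomized comparison.

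Much of this stands. It makes the predictability conditional and narrows the room for discretion. It does not remove the point, for these reasons:
- The fixed size is a stated choice, not a detail left to the manuals.
- Exclusions such as clinically significant systemic disease or a planned freeze-all cycle (Protocol 5.3.2) involve judgement.
- The order in which women are entered on the same day remains open.
- SAP Section 19.2.1 lists women outside the criteria but names no listing of eligible, consented women who were not entered, so selection could go unseen.
- Presentation by method used is a separate threat. It neither causes this one nor excuses it.

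**Conclusion.** The point holds as a cheap improvement to a stated method, with medium confidence. The share of allocations known in advance is 17% to 44% for lengths 12 down to 3 if blocks are per site and the length is known or inferred. It is under 2% with one central list over about 20 sites. The documents do not say which case applies.

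A reader might infer that sites can in fact foresee many allocations, or that the comparison is already biased. The documents do not support either reading: both conditions for foreseeability are unstated, and the plan directs that all eligible women be assigned. A reader might also take randomization to be the comparison's only protection. That goes too far, because SAP Section 14.6 plans covariate adjustment, although without the 2PN count.

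**What to change.** In Protocol Sections 5.5 and 7.3, replace the fixed block size with randomly varying block sizes that are not disclosed to sites. State whether lists are central or by centre, and keep whichever structure is already in use. Moving from a central list to lists by centre could raise predictability: about 3.9% certain for 3/6/9 within site, against 1.7% or less for a central list with fixed blocks. If lists are already by centre, prefer a larger mix: about 2% certain for 6/9/12, against about 4% for 3/6/9 and 9.5% for 3/6. Configure the data capture system to release the allocation only after Day 1 eligibility has been confirmed and locked.

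The cost is one sentence in each of two sections and a system setting, with slightly more arm imbalance at small centres. If enrolment has closed, report the block length and list structure used, and compare 2PN counts between the arms.
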